8.2.5.2 Tuberculosis management

In line with the World Health Organization (WHO) and the Centers for Disease Control and Prevention (CDC) guidelines, UCB has adopted the following definitions for latent TB, active TB and non-tuberculosis mycobacterium infection for the purposes of its clinical trials.

Latent TB

Latent TB infection is defined an infection by *Mycobacterium tuberculosis* with:

- a positive IGRA test or 2 indeterminate IGRA tests AND
- a chest x-ray [or other imaging] negative for TB infection AND
- the absence of signs, symptoms (eg, evidence of organ specific involvement, or physical findings) suggestive of TB infection.

Active TB and nontuberculous mycobacterium infection

A clinically verified case of TB meets the following criteria:

- a positive Tuberculin Skin Test (TST) or positive IGRA for *Mycobacterium tuberculosis*
- other signs and symptoms compatible with TB (eg, abnormal chest radiograph, abnormal chest computerized axial tomography scan or other chest imaging study, or other clinical evidence of active disease)

Nontuberculous mycobacterium infection (NTMBI) is defined as a clinical infection caused by mycobacterial species other than those belonging to the *Mycobacterium tuberculosis* complex. Study participants who develop active TB or NTMB infection during the study must be withdrawn from the study. The participant must be permanently discontinued from IMP and the EW Visit must be scheduled as soon as possible, but no later than the next scheduled visit.

Participants should be encouraged to enter the SFU period, attend Visit 28, and keep the EOS Visit as specified by the protocol. Treatment for active TB or NTMB should be started immediately based on local guidelines.

Confirmed active TB is always considered an SAE. UCB’s process requires that this must be captured on an SAE report form and provided to UCB in accordance with SAE reporting requirements. Follow-up reports should be completed as per protocol requirement until such time as the TB infection resolves (Appendix 3, Section 10.3).

LTB infection, active TB, or other NTMB identified during study

During TP0003, study participants who develop evidence of LTB infection, active TB, or NTMB infection will be referred to an appropriate TB specialist (pulmonologist or infectious disease specialist) for further evaluation. These study participants will not be permitted to enroll into TP0004. Study participants diagnosed with active TB or LTB infection should receive appropriate TB treatment or prophylaxis therapy. The study participant should be transferred to the care of their physician and managed according to the standard of care.

If infection with NTMB is identified during the study, the same procedure as for active TB acquired during the study and compliant TB treatment shall be followed.

Follow-up information of suspected and confirmed TB cases should be provided to UCB at least after 3, 9, and 12 months of the start date of anti-TB treatment, including hematological and biochemical safety parameters, chest x-ray evolution data, and TB diagnostic procedures used to follow up and confirm recovery of TB.

8.2.6 Splenectomized study participants

For **Japan**-specific regulations, see Appendix 8, Section 10.8.

Study participants who have previously undergone a splenectomy will be included in the study provided they do not meet the protocol defined exclusion criteria (Section 5.2) in order to optimize protection against OPSI. Adequate vaccination for all splenectomized participants within 4 years prior to enrollment is preferred. Splenectomized study participants should be vaccinated against the encapsulated organisms such as *S. pneumoniae*, *N. meningitidis*, and *H. influenzae* (as per local/or a national guidance, as applicable) as evidenced from personal immunization records. Study participants who are due to receive a booster, can be screened after they have received the required booster. However, if the next booster is due during the study, to avoid the treatment interruption, it can be given ahead of the 5-year schedule if needed, and prior to enrollment.

Splenectomized study participants without any prior vaccination against one or all of the above-mentioned bacteria and who are willing to participate in the study, will have to undergo a Prolonged Screening Period after signing the ICF. During this period, splenectomized study participants will receive the required vaccinations against the above-mentioned bacteria (see Table 1-3).

Splenectomized participants can be enrolled in the study if they have documentation of previous vaccination within the past 4 years for *S. Pneumoniae*, *H. influenzae* and *N. meningitidis* (as per local/national guidance) or have completed the required vaccinations during the Prolonged Screening Period.

Additionally, for the whole duration of the study, splenectomized participants will be required to carry a card indicating they have undergone splenectomy and may be at increased risk of infection particularly with encapsulated organisms. Splenectomized study participants should have a prophylactic antibiotic available or take already an antibiotic as per local guidance.

Antibody titers against *S. pneumoniae*, *N. meningitidis*, and *H. influenzae* in splenectomized study participants will be collected predose at W1 (Baseline), W3, W25 (EW Visit) and at the EOS Visit.

Antibody titers against tetanus will be collected in all participants at Baseline (Day1), W3 (predose), W25 (EW Visit), and EOS Visit.

8.3 Adverse events

The definitions of an AE or SAE can be found in Appendix 3, Section 10.3.

Adverse events will be reported by the study participant (or, when appropriate, by a caregiver, surrogate, or the participant's legally authorized representative).

The investigator and any designees are responsible for detecting, documenting, and recording events that meet the definition of an AE or SAE and remain responsible for following up AEs that are serious, considered related to the study treatment or study procedures, or that caused the participant to discontinue study treatment or TP0003 (see Section 7).

In order to protect the blind, the events of hypogammaglobulinemia should not be captured as an AE in the eCRF.

8.3.1 Time period and frequency for collecting AE and SAE information

All SAEs and AEs will be collected from the time of signing the ICF until the EOS Visit at the time points specified in the Schedule of Activities (Section 1.3).

All SAEs will be recorded and reported to UCB or designee within 24 hours, as indicated in Appendix 3, Section 10.3. The investigator will submit any updated SAE data to UCB within 24 hours of it being available.

The investigator is specifically requested to collect and report to UCB (or its representative) any SAEs (even if the investigator is certain that they are in no way associated with the IMP), up to 30 days from the end of the study for each participant, and to also inform participants of the need to inform the investigator of any SAE within this period. Serious AEs that the investigator thinks may be associated with the IMP must be reported to UCB regardless of the time between the event and the end of the study.

The method of recording, evaluating, and assessing causality of AE and SAE and the procedures for completing and transmitting SAE reports are provided in Appendix 3, Section 10.3.

8.3.2 Method of detecting AEs and SAEs

Care will be taken not to introduce bias when detecting AEs and/or SAEs. Open-ended and nonleading verbal questioning of the participant is the preferred method to inquire about AE occurrences.

8.3.3 Follow-up of AEs and SAEs

After the initial AE/SAE report, the investigator is required to proactively follow each participant at subsequent visits/contacts. All SAEs and nonserious AEs of special interest and AEs of special monitoring (AESM) (as defined in Sections 8.3.7 and Section 8.3.8, respectively), will be followed until resolution, stabilization, the investigator determines that it is no longer clinically significant, the event is otherwise explained, or the participant is lost to follow up (as defined in Section 7.3). Further information on follow-up procedures is provided in Appendix 3, Section 10.3.

8.3.4 Regulatory reporting requirements for SAEs

Prompt notification by the investigator to the sponsor of a SAE is essential so that legal obligations and ethical responsibilities towards the safety of study participants and the safety of a IMP under clinical investigation are met.

UCB has a legal responsibility to notify both the local regulatory authority and other regulatory agencies about the safety of a IMP under clinical investigation. UCB will comply with country-specific regulatory requirements relating to safety reporting to the regulatory authority, Institutional Review Board (IRB)/Independent Ethics Committee (IEC), and investigators.

Investigator safety reports must be prepared for suspected unexpected serious adverse reactions according to local regulatory requirements and sponsor policy and forwarded to investigators as necessary.

An investigator who receives an investigator safety report describing a SAE or other specific safety information (eg, summary or listing of SAEs) from UCB will review and then file it along with the IB and will notify the IRB/IEC, if appropriate according to local requirements.

8.3.5 Pregnancy

Details of all pregnancies in female participants and, if indicated, female partners of male participants will be collected after the start of study treatment and until 3 months after dosing.

If a pregnancy is reported, the investigator must immediately inform UCB within 24 hours of learning of the pregnancy and should follow the procedures outlined in Appendix 4, Section 10.4.

The study participant must be withdrawn from the study and permanently discontinued from IMP as soon as the pregnancy is known (by positive pregnancy test), and the following should be completed:

- The study participant should return for the EW visit and complete the SFU Period.

Abnormal pregnancy outcomes (eg, spontaneous abortion, fetal death, stillbirth, congenital anomalies, or ectopic pregnancy) are considered SAEs.

In case of confirmed pregnancy in TP0003, the study participant cannot enroll into TP0004.

8.3.6 Anticipated serious adverse events

The following anticipated SAEs are anticipated to occur in the population studied in this protocol at some frequency that is independent of drug exposure (Table 8-1).

This list does not change the investigator's obligation to report all SAEs (including anticipated SAEs) as detailed in Section 8.3.1 and Appendix 3, Section 10.3.

Table 8-1: Anticipated serious adverse events for ITP population

Anemia	Hemorrhagic events
Fatigue	Thrombocytopenia

8.3.7 Adverse events of special interest

An AE of special interest is any AE that a regulatory authority has mandated be reported on an expedited basis, regardless of the seriousness, expectedness, or relatedness of the AE to the administration of a UCB product/compound.

Potential Hy's Law, defined as $\geq 3 \times \text{ULN}$ ALT or AST with coexisting $\geq 2 \times \text{ULN}$ total bilirubin in the absence of $\geq 2 \times \text{ULN}$ ALP, with no alternative explanation for the biochemical abnormality, must ALWAYS be reported to UCB as an AE of special interest (ie, without waiting for any additional etiologic investigations to have been concluded). Follow-up information should then be reported if an alternative etiology is identified during investigation and monitoring of the participant.

See Appendix 6, Section 10.6 for further information on liver safety monitoring.

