Other Screening Tests	
 • Follicle-stimulating hormone and estradiol (as needed in women of non-childbearing potential only) • Serum or urine human chorionic gonadotropin (hCG) pregnancy test (as needed for women of childbearing potential)^h • Serology (human immunodeficiency [HIV] antibody, hepatitis B surface antigen [HBsAg], and hepatitis C virus antibody) • All study-required laboratory assessments will be performed by a central laboratory except the platelet count which is done by local laboratory. • The results of each test must be entered into the electronic Case Report Form (eCRF). 		

^a Platelet count testing will be performed by a local laboratory. Results will be unblinded to the investigator, site, and study participant (see Section 6.2.1.1).

^b International Normalized Ratio (INR) to be done only at Screening (Visit 1) and for PDILI.

^c Activated partial thromboplastin time (aPTT) and Fibrinogen will be done at all visits which require safety laboratory assessments.

^d Details of liver chemistry stopping criteria and required actions and follow-up assessments after liver stopping or monitoring event are given in Section 7.1.1 and Appendix 6, Section 10.6. All events of ALT $\geq 3x$ upper limit of normal (ULN) and bilirubin $\geq 2x$ ULN (>35% direct bilirubin) or ALT $\geq 3x$ ULN and international normalized ratio (INR) >1.5, if INR measured, may indicate severe liver injury (possible Hy's Law) and must be reported as a serious adverse event (SAE) (excluding studies of hepatic impairment or cirrhosis).

^e Includes total IgG, IgG subclasses, IgA, IgM, and IgE. Results of the IgG testing including the vaccination specific titers will be blinded to the investigator, site, and sponsor for post baseline results.

^f Local urine testing will be standard for the protocol unless serum testing is required by local regulation or Independent Review Board/Independent Ethics Committee.

Investigators must document their review of each laboratory safety report.

Laboratory/analyte results that could unblind the study will not be reported to study sites or other blinded personnel until the study has been unblinded.

10.3 Appendix 3: Adverse events – definitions and procedures for recording, evaluating, follow up, and reporting

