10.6 Appendix 6: Liver safety – suggested actions and follow-up assessments

Study treatment, including all concomitant medications and herbal supplements that are not medically necessary, should be discontinued immediately in study participants with suspected PDILI. These study participants must be assessed thoroughly and followed up closely during the Treatment Period for confirmation of PDILI. Because study participants in TP0003 will be provided the chance to enroll in the OLE study TP0004 upon completion of TP0003, if PDILI is confirmed, these study participants must not be enrolled in the OLE study TP0004.

Investigators should attempt to obtain information on study participants to complete the final evaluation.

Study participants with PDILI should not be withdrawn from the study until investigation and monitoring are complete. All results of these evaluations and observations, as well as the reason(s) for study participant withdrawal (if applicable, eg, withdrawal of consent), must be recorded in the source documents. The eCRF must document the primary reason for study withdrawal in such a case.

A specific monitoring plan must be agreed between the UCB study physician and the investigator for study participants who have ALT >5 ULN. The monitoring plan should include any necessary follow-up assessments (until resolution of the abnormal lab values).

Phase 3-4 liver chemistry stopping criteria are designed to assure participant safety and to evaluate liver event etiology ([Table 10-3](#)).

Phase 3-4 liver chemistry increased monitoring criteria with continued IMP are designed to assure participant safety and to evaluate liver event etiology ([Table 10-4](#)).

Table 10-3: Phase 3-4 liver chemistry stopping criteria and follow-up assessments

Liver Chemistry Stopping Criteria	
ALT-absolute	ALT ≥8xULN
ALT Increase	ALT ≥5xULN but <8xULN persists for ≥2 weeks ALT ≥3xULN but <5xULN persists for ≥4 weeks
Bilirubin^{a b}	ALT ≥3xULN and bilirubin ≥2xULN (>35% direct bilirubin)
INR^b	ALT ≥3xULN and international normalized ratio (INR) >1.5, if INR measured
Cannot Monitor	ALT ≥5xULN but <8xULN and cannot be monitored weekly for ≥2 weeks ALT ≥3xULN but <5xULN and cannot be monitored weekly for ≥4 weeks
Symptomatic^c	ALT ≥3xULN associated with symptoms (new or worsening) believed to be related to liver injury or hypersensitivity
Suggested Actions and Follow-Up Assessments	
Actions	Follow-Up Assessments

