
 • Immediately discontinue IMP. • Report the event to UCB within 24 hours. • Complete the liver event electronic Case Report Form (eCRF), and complete a serious adverse event (SAE) data collection tool if the event also met the criteria for an SAE.^b • Perform liver chemistry follow-up assessments. • Monitor the participant until liver chemistry test abnormalities resolve, stabilize, or return to Baseline (see MONITORING). • Do not restart/rechallenge participant with IMP unless allowed per protocol and UCB approval is granted. 
If restart/rechallenge not allowed per protocol or not granted, permanently discontinue IMP and continue participant in the study for any protocol specified follow up assessments. Consider the need for a toxicology screening.
 
MONITORING: For bilirubin or INR criteria:
	
 • Viral hepatitis serology^d • Obtain INR and recheck with each liver chemistry assessment until the transaminases values show downward trend • Only in those with underlying chronic hepatitis B at study entry (identified by positive hepatitis B surface antigen), quantitative hepatitis B deoxyribonucleic acid (DNA) and hepatitis delta antibody^e • Obtain blood sample for pharmacokinetic (PK) analysis as soon as feasible after the most recent dose^f • Serum creatine phosphokinase (CPK) and lactate dehydrogenase (LDH) • Fractionate bilirubin, if total bilirubin ≥ 2xULN • Obtain complete blood count with differential to assess eosinophilia • Record the appearance or worsening of clinical symptoms of liver injury, or hypersensitivity, on the adverse event (AE) report form

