
 Repeat liver chemistry tests (include ALT, aspartate transaminase [AST], alkaline phosphatase, bilirubin) and perform liver event follow-up assessments within 24 hours. Monitor participant twice weekly until liver chemistry test abnormalities resolve, stabilize, or return to Baseline. A specialist or hepatology consultation is recommended. 
For all other criteria
 
 Repeat liver chemistry tests (include ALT, AST, alkaline phosphatase, bilirubin) and perform liver chemistry follow-up assessments within 24 to 72 hours. Monitor participants weekly until liver chemistry abnormalities resolve, stabilize, or return to Baseline. 	
 Record use of concomitant medications (including acetaminophen, herbal remedies, and other over-the-counter medications) on the concomitant medications eCRF. Record alcohol use on the liver event alcohol intake eCRF Exclude pregnancy 
For bilirubin or INR criteria:
 
 Anti-nuclear antibody, anti-smooth muscle antibody, Type 1 anti-liver kidney microsomal antibodies, and quantitative total immunoglobulin G (IgG) or gamma globulins ^g Serum acetaminophen concentration and serum acetaminophen adduct assay (where available) for assessing the potential acetaminophen contribution to liver injury. Liver imaging (ultrasound, magnetic resonance, or computerized tomography) and/or liver biopsy to evaluate liver disease; complete Liver Imaging and/or Liver Biopsy eCRFs
---	---

^a Serum bilirubin fractionation should be performed if testing is available. If serum bilirubin fractionation is not immediately available, discontinue IMP if ALT $\geq 3xULN$ and bilirubin $\geq 2xULN$. Additionally, if serum bilirubin fractionation testing is unavailable, **record the absence/presence of detectable urinary bilirubin on dipstick**, which is indicative of direct bilirubin elevations suggesting liver injury.

^b All events of ALT $\geq 3xULN$ and bilirubin $\geq 2xULN$ (>35% direct bilirubin) or ALT $\geq 3xULN$ and INR >1.5 may indicate severe liver injury (**possible ‘Hy’s Law’**) and **must be reported as an SAE (excluding studies of hepatic impairment or cirrhosis)**. The INR measurement is not required, and the stated threshold value will not apply to participants receiving anticoagulants.

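### An AST-led potential Hy's Law case is an AE of special interest under 8.3.7, but meets no Table 10-3 stopping line and neither 'possible Hy's Law' SAE footnote, because these all name ALT only

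*Protocol*

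**What the plan says.** **The signal.** Protocol 8.3.7 defines potential Hy's Law as ALT or AST at or above 3×ULN with total bilirubin at or above 2×ULN, without ALP at or above 2×ULN and with no other explanation. Such a case "must ALWAYS be reported to UCB as an AE of special interest", without waiting for further etiologic work. The section then points to 10.6 for liver safety monitoring. SAP 10.2.2 repeats the definition.

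**The stopping rules.** In Protocol 10.6, the Table 10-3 bilirubin criterion is "ALT ≥3xULN and bilirubin ≥2xULN (>35% direct bilirubin"). The INR criterion is "ALT ≥3xULN and international normalized ratio (INR) >1.5, if INR measured". Footnote a gives a fallback: "If serum bilirubin fractionation is not immediately available, discontinue IMP if ALT" is at or above 3×ULN and bilirubin at or above 2×ULN. The attached actions, headed as suggested, include immediate discontinuation, "Report the event to UCB within 24 hours" and "Do not restart/rechallenge participant with IMP unless allowed per protocol and UCB approval is granted".

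**The SAE rule.** Footnote b of Table 10-3 says that ALT ≥3×ULN with the bilirubin condition, or with "INR >1.5 may indicate severe liver injury", is possible Hy's Law and has to be reported as an SAE. The matching footnote to Table 10-1 (10.2) says that these events "must be reported as a serious adverse event (SAE").

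**General text.** The opening of 10.6 says treatment should be stopped at once in suspected potential drug-induced liver injury (PDILI). Section 7.1.1 asks the investigator to consider stopping under Figures 7-1 and 7-2 or in the participant's best interest. Section 10.3.2 gives potential Hy's law as an example of an important medical event.

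**The concern.** The protocol uses one label, Hy's Law, with two different enzyme conditions. Section 8.3.7 counts either transaminase. The appendix it refers to, where the investigator looks for what to do next, counts ALT alone. When AST is raised to 3×ULN or more and ALT is not, the case is reportable as an AE of special interest, but no listed stopping line fits it.

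At stake is whether a case that the protocol itself treats as a serious liver signal reaches the specific actions: the immediate stop, the report within 24 hours, no restart without approval, and the explicit SAE rule. No text explains why AST counts for reporting but not for stopping or for that SAE rule. The question is participant safety and consistent reporting. No efficacy result is involved.

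**Working it through.** No published figure needs reproducing. The check sets the criteria side by side and applies them to single cases.

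**Step 1. Which enzyme each rule names.**

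| Rule | Enzyme condition | Other conditions |
|---|---|---|
| 8.3.7 potential Hy's Law | ALT or AST ≥3×ULN | total bilirubin ≥2×ULN; no ALP ≥2×ULN; no other explanation |
| Table 10-3 bilirubin stop | ALT ≥3×ULN | bilirubin ≥2×ULN, direct >35% |
| Table 10-3 footnote a | ALT ≥3×ULN | bilirubin ≥2×ULN, fractionation not immediately available |
| Table 10-3 INR stop | ALT ≥3×ULN | INR >1.5, if measured |
| SAE footnotes (Tables 10-3 and 10-1) | ALT ≥3×ULN | bilirubin ≥2×ULN with direct >35%, or INR >1.5 |
| SAP Table 10-2 (PDILI), three rows | AST or ALT >3×ULN | bilirubin >1.5×ULN; >2×ULN; >2×ULN with ALP <2×ULN |

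**Step 2. Count the Table 10-3 lines.** ALT absolute 1, ALT increase 2, bilirubin 1, INR 1, cannot monitor 2, symptomatic 1: 1 + 2 + 1 + 1 + 2 + 1 = 8. Each needs ALT of at least 3×ULN, so any case with ALT below 3×ULN meets 0 of 8 whatever its AST. Table 10-4, the increased-monitoring tier, also needs ALT ≥3×ULN.

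**Step 3. Apply the rules.** The cases are assumed. Enzymes and bilirubin are in ×ULN, at a single visit, with 50% direct bilirubin, no symptoms, weekly monitoring possible and no other explanation.

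- Case A: AST 5, ALT 2.5, bilirubin 2.5, ALP 1.2, INR 1.0. For 8.3.7: AST 5 ≥ 3, bilirubin 2.5 ≥ 2, ALP 1.2 < 2, so the pattern is met. For Table 10-3 and the SAE footnotes: ALT 2.5 < 3, so none is met.
- Case A with INR 2.0: INR exceeds 1.5, but ALT is still below 3.
- Case B: as A with the enzymes exchanged (ALT 5, AST 2.5). The bilirubin line and both SAE footnotes are met. The ALT-increase line for 5 to 8×ULN needs two weeks' persistence, so it is not met at one visit.

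| Case | 8.3.7 pattern | Table 10-3 lines now | SAE footnotes now | Lines after the fix | SAE footnotes after the fix |
|---|---|---|---|---|---|
| A | yes | 0 of 8 | 0 of 2 | 1 of 8 | 2 of 2 |
| A, INR 2.0 | yes | 0 of 8 | 0 of 2 | 1 of 8 | 2 of 2 |
| B | yes | 1 of 8 | 2 of 2 | 1 of 8 | 2 of 2 |

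The fix here adds AST to the bilirubin-linked rules only. If the INR line were extended too, A with INR 2.0 would meet 2 of 8.

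**Step 4. Does the general text reach case A?** In SAP Table 10-2, AST 5 > 3, bilirubin 2.5 exceeds 1.5 and 2, and ALP 1.2 < 2, so all three rows are met. The sponsor's analysis criteria therefore class case A as potential drug-induced liver injury, for which 10.6 says to stop.

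**Step 5. Check the reverse direction.** ALT 4, bilirubin 2.5 (50% direct), ALP 3 meets the bilirubin stop and both SAE footnotes. It fails 8.3.7 because ALP 3 ≥ 2. Neither definition contains the other.

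**The case against.** The strongest reply is that an AST-led case is not left uncovered. The opening of 10.6 says to stop at once in suspected PDILI and does not limit this to ALT. Its wording is no weaker than Table 10-3's suggested actions or than 7.1.1, where stopping is to be considered. SAP Table 10-2 shows that the sponsor counts AST. On reporting, 8.3.7 requires the AE-of-special-interest report in any event. Section 10.3.2 says that important medical events, with potential Hy's law as an example, should usually be considered serious, and 8.3.1 then applies the 24-hour limit. This stands. A reader might infer that such a participant would stay on drug or that the event would go unreported as serious; the documents do not support that. What remains is that the protocol text of 10.6 gives no laboratory definition of suspected PDILI outside its ALT-only tables, and investigators work from the protocol, not the SAP.

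The second reply is that 7.1.1 sends the investigator to Figures 7-1 and 7-2, and 7.2 makes withdrawal depend on 7.1.1. Figure 7-1 is not shown, and its abbreviation key lists AST. It may therefore contain an AST criterion. The key does not settle this, because Figure 7-2, whose title concerns ALT, also lists AST. If Figure 7-1 includes AST, it disagrees with Table 10-3 and the two still need aligning. The two SAE footnotes need the edit either way.

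A reader might also call the Table 10-3 rule simply narrower than 8.3.7. Step 5 shows otherwise: it has no ALP or alternative-cause exclusion and it adds an INR route.

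**Conclusion.** The inconsistency is real and limited. The visible texts conflict: a case with AST ≥3×ULN, ALT <3×ULN and the other 8.3.7 conditions is an AE of special interest but meets 0 of 8 Table 10-3 lines and 0 of 2 SAE footnotes. Unless Figure 7-1 covers AST, stopping rests on the general PDILI instruction in 10.6 and on investigator judgment under 7.1.1. SAE status rests on the example in 10.3.2.

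The worked cases test logic only and say nothing about frequency. A reader might infer harm to participants in this study, but the documents show none. The SAP states that the study was terminated, that nobody was randomized under Amendment 3 and that none of the 33 participants was switched to weekly dosing. The liver wording of the versions under which they were treated is not shown. The number of AST-led cases among them is not given and may be zero.

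It is also tempting to require AST in the INR line. Section 8.3.7 contains no INR condition, so it gives no support for that. The point is low priority and matters mainly if the wording is reused.

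**What to change.** Write 'ALT or AST ≥3×ULN' in four places:

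1. the Table 10-3 bilirubin criterion;
2. the fallback in Table 10-3 footnote a;
3. the bilirubin clause of Table 10-3 footnote b;
4. the bilirubin clause of the matching SAE footnote to Table 10-1.

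Then check Figure 7-1 and make it agree. Adding AST to the INR criterion is optional and would be a separate clinical decision. No change to the SAP is needed.

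This closes the AST gap but does not make the two definitions identical: the ALP and alternative-cause conditions of 8.3.7 and the direct-bilirubin condition of Table 10-3 would still differ.

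The cost is wording in four places and one figure check. Table 10-1 already collects AST, ALT, alkaline phosphatase and total and direct bilirubin, so no new sampling is needed. The downside is possibly a few more stops and SAE reports.
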